We will stratify based on education level to be largely representative of the UK population (14, 15). We will recruit (approximately):

- 50% NQF 4 Level 4 or above (University degree or equivalent) and 50% NQF Level 3 or below (no University degree)

We will also aim to fulfil the following quotas for age and gender, based on the composition of the UK population (16, 17):

- 50% 18 – 39 and 50% 40 and over
- 50% female and 50% male

We will only recruit up to 10% of the sample as current University students. Students have a high SEP in terms of education, but typically have low disposable income, which may impact relative health motives. This could distort the results if students are recruited in high numbers.

Inclusion and exclusion criteria

Participants are eligible to take part if they:

- Are a UK resident
- Are aged 18 years and above
- Are fluent in English
- Eat an out-of-home meal at least once a month on average
- Have no dietary allergies
- Are not vegan

There are no additional exclusion criteria as this is a real-world study.

Methods

Procedure

Participants will be asked to attend one session at a restaurant from Monday – Saturday between 12 – 5pm. All participants will be asked to verbally consent to taking part in the study, and will be given the opportunity to ask questions before the study begins.

Participants will be asked to order lunch from a menu. The menu will either feature nutrient warning labels next to the relevant menu items (experimental condition), or no labels (control condition). A researcher will ask participants to write their order down on an order form, communicate the order with the kitchen, photograph the meal when it is ready to be served, and photograph the plate when the participant is finished with the meal in order to estimate amount consumed.

After finishing their meal, participants will be asked to fill out an online questionnaire (on an iPad) about their sociodemographic characteristics, health motives, label awareness, salt awareness, perceived message effectiveness, perceived knowledge gain, perceived influence, and support for the introduction of a restaurant salt warning label policy in the UK. The questionnaire will also ask (i) whether any food or drink items were shared with other participants, and, if so, what item(s) were shared and (ii) whether they added any condiments to their meal (see Appendix E).

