Participants will be reimbursed with £25 for their time, as it is thought that this would cover most of their lunch, time, and travel, and would incentivise people from different SEP strata to participate. As a default, participants will:

- Pay for their meal and receive a £25 reimbursement via invoice

However, if a participant expresses that this will be an issue, they can choose to:

- Have the meal cost taken from their reimbursement. I.e., a researcher will use a prepaid card to pay for the meal. If they spend less than £25, they can opt to receive the remaining money via invoice. If they spend more than £25, they will have to pay this difference at the restaurant.

To measure food intake for the rest of the day after the intervention took place, participants will receive a link for a dietary recall questionnaire the next morning by e-mail (intake24). We will ask the

participant to complete the dietary recall questionnaire the same day they received the e-mail (i.e. the day following the intervention). Following completion, participants will be emailed a debrief form regarding the study aims (see Appendix F).

We will conduct a small pilot experiment with one table of participants ($n = 4$) prior to study commencement in order to run through the procedure with all involved researchers.

Setting

The study will be conducted in a full-service restaurant in Liverpool City Centre.

Intervention

Participants will be asked to order lunch from a menu consisting of main dishes and light bites/small plates. In the control condition, participants will be given a menu with no labels (see Figure 3). In the experimental condition, participants will be given a menu with nutrient warning labels corresponding to items that are high in salt (see Figure 4). The labels will feature beneath the menu item name and will be the same height as the name text, as per nutrient warning labelling guidelines for restaurant menus in Philadelphia (18). There will be a standard drink offering at each visit, including alcoholic drinks.

Labels will be placed next to items that exceeded 50% of the adult daily recommended limit for salt in the UK (3g) (19).

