If [yes], how would the salt label have influenced your choice? Response options: I would have avoided choosing a meal high in salt; I would have chosen a meal high in salt; Other (free text response)

Policy support

If the UK Government introduced policy requiring restaurant menu items high in salt to feature these labels, how would you feel?" Likert scale ranging from 1 – 5 anchored by "strongly oppose" and "strongly support".

Control: Same as above

Additional thoughts on label

"Please use this box to add any additional thoughts which you may have about the salt label" (open text response).

Control: Same as above

Secondary outcomes

Total salt purchased

Determined based on the total order of the participant, including food and drink. Prior to study commencement, all menu items will be sent for nutritional analysis to determine salt content/100g. Menu items will be weighed before being sent for analysis using kitchen scales (Vitafit VT706), so that specific salt content per serving can be calculated.

Labelled item selected

Determined based on whether the food item selected featured a high in salt warning label (yes = 1, no = 0).

Total salt consumed

Salt consumption will be determined from the order that the researcher takes and an estimation of the proportion of the meal that was consumed. The researcher will take a photograph before and after consumption and will estimate the percentage consumed component(s) of the meal, taking into account whether participants leave a proportion of all meal components or specific components (e.g., low salt or high salt components). Participants will also be asked whether they shared any of their meal with someone else. A random 10% selection of percentage estimates will be performed by a second researcher to measure reliability. Food consumption will then be calculated by subtracting an estimation of the proportion of the meal that was consumed (taking into account if any has been shared) from the food purchase.

Later salt intake

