Reimbursement	
 - Participants will receive £25 which will likely cover their lunch costs and serve as an incentive for people from different SEP strata to participate. Participants will either (i) pay for their own meal at the restaurant and receive £25 via invoice or (ii) have their meal paid for by a researcher using a prepaid card; if this costs less than £25, they can request to receive the remaining amount via invoice, if this costs more than £25, they will need to pay the difference at the restaurant. 	

Statistical analysis

Participant characteristics

Participant characteristics will be presented overall and by experimental condition in a table. Data will include age, gender, ethnicity, highest educational qualification, employment status, BMI, frequency of eating OOH, and hunger. Continuous variables will be summarised as means and standard deviations, and categorical variables will be summarised as counts and percentages.

Measured variables

Primary

A linear regression will be used to assess differences between menu conditions in terms of PME. The between-subjects predictor will be label condition, and the dependent variable will be PME.

Highest education level (categorical: NQF level 4 or above, NQF level 3 or below) will be included as a covariate in the model to account for stratification (30). Health motives (continuous) will be included as a covariate as this may predict outcomes (e.g., health motivated individuals may be more likely to believe a menu with labels will change their behaviour) (30). Age and gender will also be included as covariates as previous work suggests that this can influence ratings of label PME and salt intake (13).

Descriptive analysis will be used to report (overall and by condition) participants' label awareness, salt awareness, perceived knowledge gain, perceived influence, and policy support (dichotomised into support/oppose). Logistic regressions will be performed to assess the odds of (i) being aware of the label, and (ii) being aware of the salt content of the meals in the labelled menu group, using the control menu group as the reference category. The same covariates as above will be included.

Secondary

Linear regressions will be performed to assess differences in menu conditions in terms of total salt purchase and total salt intake. The same covariates as above will be included.

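### The derivation sentence for total salt consumed is inverted: as written it gives the food salt not eaten (minor drafting correction)

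*Combined protocol and SAP*

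**What the plan says.** Under Measures, Secondary outcomes, the paragraph on total salt consumed opens with the inputs: "Salt consumption will be determined from the order that the researcher takes and an estimation of the proportion of the meal that was consumed". It then describes before and after photographs, a researcher's estimate of the percentage eaten by meal component, and a question about sharing. It closes with the only arithmetic given: "Food consumption will then be calculated by subtracting an estimation of the proportion of the meal that was consumed", allowing for sharing, from the food purchase. The Procedure section gives the purpose of the photographs; the researcher will "photograph the plate when the participant is finished with the meal in order to estimate amount consumed".

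Total salt purchased is defined just above, on the whole order, food and drink together. Its salt values come from laboratory analysis: "all menu items will be sent for nutritional analysis to determine salt content/100g". The analysis section then states: "Linear regressions will be performed to assess differences in menu conditions in terms of total salt purchase and total salt intake".

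Other macronutrient intake (kcal, sugar, saturated fat) is derived from the nutritional content of the order, with no allowance for leftovers or sharing. The Exploratory analyses section treats it as intake.

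**The concern.** Subtracting what was eaten from what was bought leaves what was not eaten. The last sentence of the paragraph therefore defines the complement of the outcome named in its heading. Total salt intake is a stated secondary objective with its own regression, tested at alpha .05. No other part of the document gives a formula that would override the sentence.

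If it were programmed literally, the variable would measure leftovers and food given away. An effect of the labels on intake could then appear much smaller than it is, or with the opposite sign.

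The macronutrient variables have a milder form of the same mismatch between name and derivation. A value computed from the order cannot show a change in how much was eaten, yet it is analysed under the name intake.

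**Working it through.** **The plan's own figure.** The Sample size section gives 260 participants (130 per condition) for d = 0.35, 80% power, two-tailed; alpha is .05. The normal approximation gives 2 x (1.960 + 0.842)² / 0.35² = 128.2, so 129 per arm and 258 in total. The t-based calculation gives 129.1, so 130 per arm and 260 in total, with power 0.803. The figure reproduces and does not depend on how intake is derived.

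**Inputs.** S is the salt in the food ordered. The illustration uses 3 g, the threshold above which an item is labelled (Intervention section). p is the proportion eaten by the participant. The documents give no values for p, so every p below is an assumption.

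**Formulas.** Intake = pS. Sentence as written = S - pS = (1-p)S. They are equal only when p = 0.5 (or S = 0).

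**One participant, S = 3 g:**
- p = 1.0: intake 3.0 g, as written 0 g
- p = 0.9: intake 2.7 g, as written 0.3 g
- p = 0.8: intake 2.4 g, as written 0.6 g
- p = 0.5: intake 1.5 g, as written 1.5 g

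Subtracting the bare proportion from grams does not rescue the sentence: 3 - 0.8 = 2.2 mixes units and is not the intake of 2.4 g.

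**Arm difference (label minus control), same p for everyone.** The difference as written is (1-p)/p times the true one. Suppose mean food salt ordered is 3.5 g in control and 3.0 g with labels (assumed):
- p = 0.8: true 0.8 x (3.0 - 3.5) = -0.40 g; as written 0.2 x (-0.5) = -0.10 g; ratio 0.2/0.8 = 25%
- p = 0.9: true -0.45 g; as written -0.05 g; ratio 0.1/0.9 = 11%

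**Arm difference, same order, different p.** Suppose 3 g is ordered in both arms, with 90% eaten in control and 80% with labels (assumed). The true difference is 2.4 - 2.7 = -0.3 g. As written it is 0.6 - 0.3 = +0.3 g, so the sign reverses.

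**Regression coefficients.** Because (1-p)S = S - pS and least squares is linear in the outcome, the label coefficient as written equals the food-purchase coefficient minus the food-intake coefficient, given the same participants and covariates. This holds for food salt. It does not hold exactly against the planned purchase outcome, which includes drinks. Under the mixed model planned if clustering is found, it is only approximate, because the variance components are re-estimated for each outcome.

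**Other macronutrients.** No arithmetic is needed. The stated derivation uses the order only, while the variable's name and its use in the exploratory analysis refer to intake.

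**The case against.** The strongest reply is that nobody would be misled. The paragraph's heading, its opening sentence and the purpose of the photographs all point to the amount eaten. The sentence also mixes a proportion with a purchase, so a programmer has to interpret it before coding anything. Cleared plates scoring zero would be noticed, and the raw inputs are kept, so the outcome could be recomputed. All of this stands, and it is why the point is minor. It does not remove the point: the opening sentence names inputs but no operation, and a pre-specified derivation should not depend on the analyst overriding it.

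It is also fair that the illustrated sizes rest on assumed proportions, and that the 25% and 11% ratios need everyone to eat the same share. They show what the formula does and do not predict a bias.

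Drinks limit both the criticism and the remedy. The photographs and percentage estimates concern the meal, and nothing describes estimating how much of a drink was consumed. A plate-based proportion should therefore not be applied to a total that includes drinks.

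A reader might infer that leaving condiments out of the definition is a further error, because Appendix E records them in teaspoons and gives salt as an example. The documents do not support that. The definition lists its inputs and condiments are not among them; counting or not counting them are both defensible.

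**Conclusion.** The sentence is wrong as written and needs correcting. The algebra, (1-p)S in place of pS, needs no assumption beyond reading the proportion as a share of the food purchase. The gram values and arm differences are illustrative only. The kcal, sugar and saturated fat variables are mislabelled for what they compute; they are exploratory, tested at alpha .01, so little hangs on them.

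A reader might go further and conclude that the trial will report leftovers as intake, or that its main conclusions are at risk. The documents do not support either. The intended derivation is evident and the data needed for it are collected. PME does not use this variable, the sample size reproduces without it, and the interim decision rests on PME and the odds of choosing a high-salt meal. Severity: minor correction.

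**What to change.** Replace the closing sentence with: *Food salt consumed = salt in the food ordered x proportion eaten by the participant (proportion gone from the plate minus the reported proportion given to others), by component where component values exist.* Then state whether drinks are added as ordered or left out.

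For kcal, sugar and saturated fat, either apply the same food proportions, with drinks as ordered, or rename the variables as nutrients ordered, both in Measures and in Exploratory analyses. Renaming is enough. Optionally, add one sentence saying whether condiment salt counts.

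The cost is a few sentences and no new data. Three limits should be accepted openly:
- The plan describes laboratory analysis of menu items and does not mention components, so the component step applies only where such values exist.
- Appendix E asks how much of each item was shared without saying that this means given away, so that reading should be stated.
- Food received from others at the table would still not be credited.

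If condiments are counted, standard salt values from outside the trial are needed, and self-reported teaspoons will add noise.

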To date, the impact of nutrient warning labels has not been tested in a real-world randomised controlled trial (i.e., in a restaurant), or in a UK context. Recent work suggests that UK consumers support the introduction of nutrient warning labels, and their PME was rated as significantly higher relative to a control label (QR code) (13). This study aims to test the effect of a menu featuring salt warning labels (design informed by previous work (13)) on perceived message effectiveness relative to a menu with no labels in a real-world restaurant environment. The study will also act as a pilot experiment for examining the impact of the salt warning label on food choice and subsequent salt intake in real-world conditions.

Primary objectives:

- To measure the PME of a menu featuring salt warning labels relative to a menu with no labels
- To measure label awareness, perceived knowledge gain, and perceived influence of the label on food choice

Secondary objectives:

- To identify whether there is an effect of the salt warning label on:
 - Food choice (label/no label)
 - Total salt selected
 - Total salt intake
- To examine support for the introduction of a salt warning label policy in the UK

Experimental design

The study will be a between-subjects randomised controlled trial design. The between-subject factor is the menu labelling. In the experimental condition, a nutrient warning label will be placed next to menu items that are high in salt. In the control condition, there will be no labels. The outcome will be (i) perceived message effectiveness, (ii) salt selected, label (y/n) selected, and salt intake. This will allow us to examine whether the salt warning label intervention impacts perceived message effectiveness and food choice relative to the control condition.

Participants and recruitment

Recruitment

Participants will be recruited via social media adverts (Facebook, Instagram), a database maintained by researchers at the University of Liverpool, and word of mouth. Interested participants will be asked to click a link which will take them to an online screening questionnaire (Appendix A). Participants can bring a maximum of nine guests to the restaurant. Guests will be pre-screened in advance to ensure eligibility. In pre-study instructions participants will be informed that any guests they bring will participate in the study.

Sampling

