Participant groups will be randomised to either the experimental or control condition using a block randomisation schedule (<https://www.sealedenvelope.com/simple-randomiser/v1/lists>). Participants seated at the same table will be in the same condition. Therefore, to adjust for possible differences in group sizes and consequently numbers in each condition, we will randomise in blocks of 50. The menu contains eight main dishes and eight light bites/small plates (five of which are high in salt).

Figure 3: Menu (A) for the control condition

ME NU

EVERYDAY FROM 11.30AM

Light Bites/Small Plates

Mushroom Soup served with crusty bread and butter	£5.50
Cajun Chicken Flatbread Flatbread filled with Cajun Chicken, roasted pepper, herb salad & lime mayonnaise	£7.95
Beetroot Hummus Flatbread Flatbread served with Hummus, house salad & pomegranate dressing	£6.95
Ruban Toasted sandwich Sliced pastrami, Baltic pickles, Sauerkraut with melted Gruyere	£8.95
Mexican Cheese on toast A blend of melted cheese, chillies and spring onion	£5.95
Loaded Dirty Fries Melted cheese, Baltic chilli and BBQ sauce - Add Chicken or Halloumi for £1.50	£5.95
Loaded Dirty Fries with chicken Melted cheese, Baltic chilli and BBQ sauce - Add Chicken or Halloumi for £1.50	£7.45
Loaded Dirty Fries with halloumi Melted cheese, Baltic chilli and BBQ sauce - Add Chicken or Halloumi for £1.50	£7.45

Mains

Chefs Homemade Scouse Served with crusty bread, pickled cabbage and beetroot	£8.50
Steak & Ale Pie Served with house fries and mushy peas	£11.50
Baltic Black & White Burger Black Burger Bun, Grilled Halloumi, peppers, tomato, lettuce, chilli BBQ relish served with house fries	£10.00
6oz Baltic Cheese Burger A 6oz burger patty, Brioche bun, lettuce, tomato served with burger relish & House fries	£10.95
Steak & Eggs Hash Grilled 4oz Ribeye steak, creamy peppered hash potatoes topped with fried egg	£11.50
Super Food Salad Baltic house salad, quinoa, pomegranate, tenderstem Broccoli, cucumber, tomato, red onion served with Soy honey dressing Add Chicken or Halloumi for £1.50	£7.95
Super Food Salad with chicken Baltic house salad, chicken, quinoa, pomegranate, tenderstem Broccoli, cucumber, tomato, red onion served with Soy honey dressing	£9.45
Super Food Salad with halloumi Baltic house salad, halloumi, quinoa, pomegranate, tenderstem Broccoli, cucumber, tomato, red onion served with Soy honey dressing	£9.45

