Information sheet and informed consent	
 - Eligible participants will be e-mailed an information sheet (Appendix B) and consent form (Appendix C). Participants can ask any questions about the study via e-mail. - The researcher will schedule a study visit day, leaving 30-minute gaps between participant groups. Participants may bring a maximum of nine guests aged 18 years or older to the restaurant. - As the guests did not yet receive an online information sheet and consent form, all participants will also be provided with information by the researcher and provide verbal consent. The researcher will answer any questions prior to the study. 				
Meal choice task	
 - Participants will be invited to visit the restaurant. They will be assigned in advance to either the control or experimental condition. Any guests will be in the same condition as the primary participant (i.e., participants will be randomised by table). They will also be given a participant number which they will be required to enter in any questionnaire they complete. 				
	
  
 Control condition	Experimental condition	
   
  
 - Participants will receive a standard menu without nutrient warning labels. 	 
 - Participants will receive a menu featuring a nutrient warning label next to items high in salt. Text at the bottom of the menu will read “[label image] indicates that the salt content of this item is higher than 50% of the daily recommended limit (6g per day). High salt 	
  
	Control condition	Experimental condition	
 - Participants will receive a standard menu without nutrient warning labels. 	
 - Participants will receive a menu featuring a nutrient warning label next to items high in salt. Text at the bottom of the menu will read “[label image] indicates that the salt content of this item is higher than 50% of the daily recommended limit (6g per day). High salt
Control condition	Experimental condition				

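### Tables are allocated before the visit and verbal consent, and no concealment from those who book, screen or take consent is described

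*Combined protocol and SAP*

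**What the plan says.** **Sequence.** The Intervention section states: "Participant groups will be randomised to either the experimental or control condition using a block randomisation schedule". It adds "we will randomise in blocks of 50" to allow for unequal group sizes. A list-generating website is named. Nothing is said about who holds the list or who may look at it.

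**Timing of allocation.** The Meal choice task row of the Study flow table states: "They will be assigned in advance to either the control or experimental condition". Guests take the primary participant's condition, so the table is the randomised unit.

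**Who joins the table, and when.** Recruitment allows up to nine guests and says: "Guests will be pre-screened in advance to ensure eligibility". The Information sheet and informed consent row of the Study flow says: "The researcher will schedule a study visit day, leaving 30-minute gaps between participant groups". That row has eligible participants emailed an information sheet and consent form. It notes that guests will not have had these, so "all participants will also be provided with information by the researcher and provide verbal consent". The Procedure section places verbal consent within the restaurant session, before the study begins.

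**What diners are told.** Under Aim guessing, participants are told only that the study concerns dining habits in restaurants.

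**The concern.** When whole tables are randomised, the comparison is protected only if who enters each table cannot depend on the table's condition. Here the condition is set before the visit, while agreement to take part, for guests their first, is sought afterwards by the researcher. If that researcher can see the allocation, the way the study is explained, a refusal is accepted or a booking is handled could differ by arm, even without intent.

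A difference arising this way falls on the randomised comparison for perceived message effectiveness (PME), the outcome for which the study is powered. The planned covariates (education, health motives, age and gender) would remove only the part that runs through those traits. The plan also gives no rule for tables or guests who cancel, are added or refuse between assignment and ordering. The interim trigger in the Sample size section counts completers per condition, so such losses need not become visible.

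**Working it through.** This is mainly a matter of order and of what is described, so the steps are set side by side.

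| Step | Where stated | Order relative to allocation |
|---|---|---|
| Emailed information and consent form, primary participant | Study flow, consent row | Not stated |
| Scheduling of the visit | Study flow, consent row | Not stated |
| Guest screening | Recruitment | Before the visit; order against allocation not stated |
| Allocation | Study flow, Meal choice row | Before the visit |
| Verbal consent from all diners, first consent for guests | Procedure; Study flow, consent row | After: it takes place in the session |
| Concealment of the list | Nowhere | Not described |

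The row order of the Study flow does not settle the open entries. Its consent row includes verbal consent, which the Procedure puts in the session, yet that row precedes the one containing the advance assignment. The table is therefore not a strict chronology. One ordering is firm: allocation comes before the visit, and verbal consent comes at it.

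**The plan's own figure.** The sample size is not in question and reproduces. With d = 0.35, two-sided alpha 0.05 and 80% power, n per arm = 2 × (1.960 + 0.842)² / 0.35², about 128, rounded up to 129 (258 in total). The exact t-test gives 129.1, rounded up to 130 per arm, or 260, as stated.

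**Scale, by assumption only.** The documents give no figure for selection, so the following shows sensitivity and estimates nothing. Independent diners are assumed and clustering by table is ignored. At 130 per arm the standard error of the difference in SD units is √(2/130) = 0.124. With no true effect, if selection shifts the arms apart by b SD, the two-sided type I error is Φ(b/0.124 − 1.96) + Φ(−b/0.124 − 1.96):

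- b = 0.05: 0.069
- b = 0.10: 0.127
- b = 0.15: 0.227
- b = 0.20: 0.364

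If a fraction f of one arm is lost and those lost differ by m SD from that arm's average, the shift is b = m × f/(1 − f):

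- f = 0.10, m = 0.5: b = 0.5 × 0.1/0.9 = 0.056, type I error 0.073
- f = 0.20, m = 0.5: b = 0.5 × 0.2/0.8 = 0.125, type I error 0.172

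A larger sample does not help. At 250 per arm (half the stated maximum of about 500), b = 0.10 gives 0.201 instead of 0.127.

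**The case against.** The strongest reply is that the plan already limits the ways in which selection could occur. Guests are screened in advance. Primary participants receive written information before the visit. Diners have a neutral account of the purpose, so cancellations or refusals by people unaware of their condition cost numbers but do not in themselves bias the comparison. Blocks of 50 make the next allocation hard to guess. Bias therefore needs a researcher who knows the condition and acts on it, and the plan does not say that anyone who books or takes consent has that knowledge. Characteristics will be tabulated by condition, which would expose gross imbalance in measured traits.

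All of this stands, and it narrows the point to the researcher's possible knowledge of the allocation. It does not remove it. The neutral purpose blinds diners, not staff. A large block prevents guessing but not reading a visible list. Tabulation shows measured traits only.

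A reader might infer that scheduling and guest lists are still open when a table is assigned, so that researchers fill a slot knowing its condition. The text does not support that: advance assignment means before the visit, and its order against booking and guest screening is not given. Nor do the documents describe substitution or late additions. A reader might equally infer that the team knows the condition when it takes consent; the plan is silent on this.

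**Conclusion.** The concern holds in a limited form. By the plan's own sequence, diners at a randomised table give verbal consent after allocation, for guests their first consent, and no concealment of the list is described. The right statement is that no protection is described, not that protection is known to be absent or that selection has occurred.

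The size of any bias cannot be estimated from the documents, and the figures above rest wholly on assumed shifts and losses. They show only that small shifts matter little (0.05 SD moves the type I error from 0.05 to about 0.07) and that moderate ones would matter (0.10 SD, to about 0.13). This is a cheap improvement to the protection of the primary comparison. No stated number is wrong.

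**What to change.** Replace the advance-assignment sentence in the Study flow with wording such as: *the next allocation on the pre-generated list is revealed only when the group is seated and every diner has given verbal consent.*

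- Use sequentially numbered opaque envelopes, each holding the condition and the matching A/B stickers that the Appendix E questionnaire relies on.
- Take table membership as fixed at the moment of reveal, and analyse tables as allocated from then.
- Report, by arm, tables and diners allocated, refusing and analysed. Report refusals before reveal separately, without arm.

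This settles the matter whichever order of booking, screening and allocation was intended. It does not address what the researcher knows once menus are handed out, which is a separate question.

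The cost is a change of protocol wording, preparation of the envelopes, and both menu sets and sticker sets kept ready on site and chosen on arrival instead of laid out beforehand. The sample size is unchanged, and the step itself should need no extra staff.
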